4.5.2.2 Central Laboratory Assessments

The following samples will be sent to one or several central laboratories or to the Sponsor for analysis:

- Serum samples for atezolizumab PK analysis through use of a validated assay
- PBMC and plasma samples for cobimetinib PK analysis through use of a validated assay
- Serum samples for assessment of anti-drug antibodies (ADAs) to atezolizumab through use of a validated assay
- Plasma and blood samples for exploratory research on biomarkers
- Archival (most recently obtained [< 5 years old]) or fresh tumor tissue sample consistent with the patient's diagnosis, collected at baseline for determination of *BRAF*^{V600}-mutation status and for exploratory research on biomarkers

A representative formalin-fixed paraffin-embedded tumor specimen in a paraffin block (preferred) or 20 slides containing unstained, freshly cut, serial sections must be submitted along with an associated pathology report prior to study start.

Samples must contain a minimum of 50 viable tumor cells that preserve cellular context and tissue architecture regardless of needle gauge or retrieval method. Tumor tissue should be of good quality based on total and viable tumor content. Acceptable samples include those from resections, core-needle biopsies (at least three cores, embedded in a single paraffin block), or excisional, incisional, or forceps biopsies. Fine-needle aspiration (defined as samples that do not preserve tissue architecture and yield cell suspension and/or smears), brushing, cell pellets from pleural effusion, and lavage samples are not acceptable. Tumor tissue from bone metastases that have been decalcified is not acceptable.

If 20 slides are not available or the tissue block is not of sufficient size, the patient may still be eligible for the study after discussion with and approval by the Medical Monitor. If archival tissue is unavailable or unacceptable, a pretreatment tumor biopsy is required.

For archival samples (< 5 years old), remaining tumor tissue blocks for enrolled patients will be returned to the site upon request or 18 months after final closure of the study database, whichever occurs first. Remaining tumor tissue blocks for patients who are not enrolled in the study will be returned to the site no later than 3 months after eligibility determination. Slides will not be returned.

- For patients in Cohorts A and C, optional tumor tissue samples collected at the time of progression, if deemed clinically feasible by the investigator, for exploratory research on biomarkers

Biopsies should be performed at the time of progression, preferably within 3 days after the last dose of study treatment. Acceptable samples include those from resections, core-needle biopsies (three cores preferred), or excisional, incisional, or forceps biopsies.

- For Cohort A patients, an optional biopsy can also be collected 4–6 weeks after the first atezolizumab dose.
- For patients enrolled in Cohort B, the biopsy cohort will undergo biopsies according to the following schedule:

A mandatory predose biopsy will be obtained before Cycle 1, Day 1.

A mandatory on-treatment biopsy will be obtained between Days 10 and 14 of Cycle 1.

A second, optional, on-treatment biopsy will be obtained during Cycle 2, after the second dose of atezolizumab, to assess the combined effects of cobimetinib and atezolizumab.

A mandatory biopsy at the time of progression

Biomarker research may include, but will not be limited to, analysis of S100, ctDNA, genes or gene signatures associated with tumor immunobiology, tumor immune profiles (e.g., CD8, MHC, and PD-L1), lymphocytes, or TCR repertoire and may involve DNA or RNA extraction, analysis of somatic mutations, and use of NGS (see [Table 4](#)). An optional blood sample for WGS may also be obtained.

Table 4 Proposed Biomarkers for Exploratory Research

Sample Type	Timing	Proposed Biomarker(s)
Plasma	Predose on Day 1 of Cycles 1, 2, at time of subsequent radiologic tumor assessments, and at disease progression	
 • S100 • ctDNA
PBMC	Predose on Day 1 of Cycles 1, 2, and at time of subsequent radiologic tumor assessments, and at disease progression	
 • TCR repertoires
Tumor tissues	Prior to study: archival (< 5 years old) or at baseline (required)	
 • Tumor mutations • Tumor-immune contexture, such as PD-L1, MHC1, and CD8⁺ T cells
Tumor biopsy	On-treatment (optional) and time of disease progression (required if clinically feasible)	
 • Tumor-immune contexture, such as PD-L1, MHC1, and CD8⁺ T cells
DNA and RNA extracted from tumor tissues, plasma and PBMC	Same as tumor tissue and biopsy	
 • Mutation load/profiles in DNA • TCR profiles in DNA • Immuno-signatures by RNA expression

ctDNA= circulating tumor DNA; MHC1= major histocompatibility complex class I; PBMC= peripheral blood mononuclear cell; PD-L1 = programmed death–ligand 1; TCR=T-cell receptor.

NGS may be performed by Foundation Medicine. If performed by Foundation Medicine, the investigator can obtain results from these analyses in the form of an NGS report, which is available upon request directly from Foundation Medicine. The investigator may share and discuss the results with the patient, unless the patient chooses otherwise. The Foundation Medicine NGS assay has not been cleared or approved by health authorities. The NGS report is generated for research purposes and is not provided for the purpose of guiding future treatment decisions.

For sampling procedures, storage conditions, and shipment instructions, see the laboratory manual.

Biologic samples will be destroyed when the final Clinical Study Report has been completed, with the following exceptions:

- Plasma and serum samples collected for PK analysis or immunogenicity analysis may be needed for additional immunogenicity characterization and PK and immunogenicity assay development and validation; therefore, these samples will be destroyed no later than 5 years after the final Clinical Study Report has been completed.
- Blood samples collected for WGS will be stored until they are no longer needed or until they are exhausted.
- Blood and tissue samples collected for biomarker analyses will be destroyed no later than 5 years after the final Clinical Study Report has been completed, or earlier, depending on local regulations.

When a patient withdraws from the study, samples collected before the date of withdrawal may still be analyzed, unless the patient specifically requests that the samples be destroyed or local laws require destruction of the samples. However, if samples have been tested prior to withdrawal, results from those tests will remain as part of the overall research data.

Data arising from sample analysis will be subject to the confidentiality standards described in Section [8.4](#).

Given the complexity and exploratory nature of exploratory biomarker analyses, data derived from these analyses will generally not be provided to study investigators or patients unless required by law (with the exception of the report from Foundation Medicine). The aggregate results of any conducted research will be available in accordance with the effective Sponsor policy on study data publication.

4.5.3 Study Treatment Discontinuation

Patients must permanently discontinue study treatment if they experience any of the following:

- Clinical deterioration due to disease progression
- Any adverse event that requires study treatment discontinuation per the guidelines in [Appendix 7](#).
- Use of a non-protocol-specified anti-cancer therapy
- Intolerance of study treatment despite undergoing protocol-defined dose reduction
- Pregnancy
- Withdrawal of consent
- Any medical condition that the investigator or Sponsor determines may jeopardize the patient's safety if he or she continues to receive study treatment

- Investigator or Sponsor determines it is in the best interest of the patient (e.g., unwillingness to comply with study assessments that compromise their safety)

Patients who discontinue study drug for any reason will be asked to return to the clinic for a treatment discontinuation visit 30 (\pm 3) days after the last dose of study drug. The visit at which response assessment shows disease progression may be used as the treatment discontinuation visit, provided all required assessments have been performed and it is 30 (\pm 3) days after the last dose of study drug. The primary reason for study treatment discontinuation should be documented on the appropriate eCRF. Patients who discontinue study treatment will not be replaced.

After treatment discontinuation, information on survival follow-up and subsequent anti-cancer therapy will be collected via telephone calls, patient medical records, and/or clinic visits approximately every 12 weeks until death (unless the Sponsor terminates the study). If the patient withdraws from the study, the study staff may use a public information source (e.g., county records) to obtain information about survival status only as is permissible per local laws and regulations.

4.5.4 Study and Site Discontinuation

The Sponsor has the right to terminate this study at any time. Reasons for terminating the study may include, but are not limited to, the following:

- The incidence or severity of adverse events in this or other studies indicates a potential health hazard to patients.
- Patient enrollment is unsatisfactory.

The Sponsor will notify the investigator if the Sponsor decides to discontinue the study.

The Sponsor has the right to close a site at any time. Reasons for closing a site may include, but are not limited to, the following:

- Excessively slow recruitment
- Poor protocol adherence
- Inaccurate or incomplete data recording
- Non-compliance with the International Council for Harmonisation (ICH) guideline for Good Clinical Practice
- No study activity (i.e., all patients have completed the study and all obligations have been fulfilled)

5. ASSESSMENT OF SAFETY

5.1 SAFETY PLAN

The safety plan for patients in this study is based on clinical experience with cobimetinib and atezolizumab in completed and ongoing studies and on published data from similar molecules. The anticipated important safety risks for cobimetinib and atezolizumab are

outlined below. Refer to the Cobimetinib Investigator's Brochure and Atezolizumab Investigator's Brochure for a complete summary of safety information.

Measures will be taken to ensure the safety of patients participating in this study, including the use of stringent inclusion and exclusion criteria and close monitoring of patients during the study. Eligibility criteria have been designed to exclude patients at higher risk for toxicities. Administration of atezolizumab will be performed in a monitored setting in which there is immediate access to trained personnel and adequate equipment and medicine to manage potentially serious reactions.

Patients will undergo safety monitoring during the study, including assessment of the nature, frequency, and severity of adverse events. In addition, guidelines for managing adverse events, including criteria for dosage modification, and treatment interruption or discontinuation, are provided below. There are separate guidelines for the three different arms as the toxicities and management guidelines are distinct. Refer to the specific guidelines for each arm individually.

The risks associated with cobimetinib and atezolizumab are detailed in Section 5.1.1 and 5.1.2, respectively. Additional information on the risks of atezolizumab and management of atezolizumab-related adverse events are outlined in Appendix 8

Adverse events will be reported as described in Sections 5.2–5.4. Oversight will be provided by the Medical Monitor and drug safety personnel.

5.1.1 Risks Associated with Cobimetinib

The information related to the risks attributed to cobimetinib is based on safety data from Studies GO28141, NO25395, and MEK4592g. Additional clinical experience has been obtained through postmarketing experience and clinical studies with cobimetinib in combination with other agents. The safety data are also based on postmarketing experience. For further information regarding clinical safety, refer to the current Cobimetinib Investigator's Brochure.

5.1.1.1 Important Identified Risks Associated with Cobimetinib **5.1.1.1.1 Hemorrhage**

Hemorrhage, including major hemorrhages, defined as symptomatic bleeding in a critical area or organ, can occur with cobimetinib. In clinical studies with cobimetinib, events of cerebral hemorrhage, gastrointestinal tract hemorrhage, reproductive tract hemorrhage, and hematuria, have been reported.

In Study GO28141, Grade 1–4 hemorrhagic events were reported in 13.0% of patients treated with cobimetinib plus vemurafenib and in 7.3% of patients treated with placebo plus vemurafenib. The majority of hemorrhagic events were Grade 1 or 2 and non-serious. Grade 3 and 4 hemorrhage events were reported in 1.2% of patients

receiving cobimetinib plus vemurafenib and in 0.8% of patients receiving placebo plus vemurafenib.

Caution should be used in patients with additional risk factors for bleeding, such as brain metastases, and/or in patients that use concomitant medications that increase the risk of bleeding (including antiplatelet or anticoagulant therapy).

Instructions for dose modification for hemorrhagic events are included in Section [5.1.3.3](#).

5.1.1.1.2 Serous Retinopathy

Serous retinopathy is a known adverse effect of cobimetinib and has also been observed with other MEK inhibitors (refer to Section [3.3.7](#) for details).

To address serous retinopathy with cobimetinib treatment, all patients are required to undergo ophthalmologic examination at baseline and at specified timepoints throughout the study. Details regarding baseline and subsequent ophthalmologic examinations are provided in Section [4.4.7](#).

Guidelines for management of patients who develop Grade ≥ 2 visual disorders or retinopathy are provided in Section [5.1.3.3](#).

5.1.1.1.3 Left Ventricular Dysfunction

Decreases in LVEF from baseline have been reported in patients receiving cobimetinib. Left ventricular dysfunction may occur with signs and symptoms of cardiac failure, or reduction in LVEF events may be asymptomatic.

Left ventricular dysfunction has been characterized in Study GO28141. The study incorporated prospective serial LVEF evaluations in all patients. With active surveillance, measured Grade 2 or 3 reductions in LVEF were observed more frequently in patients treated with cobimetinib plus vemurafenib than placebo plus vemurafenib (8.5% vs. 3.7%, respectively). Of the patients treated with cobimetinib plus vemurafenib, 2 patients (0.8%) had symptomatic reduction in LVEF and the remaining patients were asymptomatic. Most LVEF reduction events in patients on cobimetinib plus vemurafenib (62%) improved or resolved with management according to dose modification guidelines (see in Section [5.1.3.3](#)).

5.1.1.1.4 Rhabdomyolysis and CPK Elevations

Elevations in CPK have been observed in patients who received cobimetinib monotherapy as well as when administered with other agents. The majority of CPK elevations reported was asymptomatic, non-serious, and resolved with or without study drug interruption. One event of rhabdomyolysis was reported in the Phase III study GO28141 (cobimetinib plus vemurafenib), and rhabdomyolysis has been reported in the postmarketing experience.

In Study GO28141, elevated CPK was reported as an adverse event more frequently in patients treated with cobimetinib plus vemurafenib (32.4% all grades, 11.3% Grade ≥ 3 events) than placebo plus vemurafenib (8.1% all grades, 0% Grade ≥ 3 events).

CPK will be monitored at baseline and monthly during treatment or as clinically indicated.

5.1.1.1.5 Liver Laboratory Abnormalities

Liver laboratory abnormalities can occur when cobimetinib is used with vemurafenib.

Liver laboratory abnormalities, specifically increases in ALT, AST, and ALP, have been observed in patients treated with cobimetinib and vemurafenib.

Liver laboratory tests should be monitored before initiation of treatment and monthly during treatment, or more frequently as clinically indicated.

Grade 3 and 4 liver laboratory abnormalities should be managed with dose interruption, reduction, or discontinuation of cobimetinib.

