4.2.2 Dosage, Administration, and Compliance

4.2.2.1 Cobimetinib

Patients in Cohorts A and B will receive 60 mg (3 tablets of 20 mg each) orally QD for Days 1–21 of each 28-day cycle. This 4-week period is considered a treatment cycle.

Cobimetinib should be taken at the same time every day. It can be taken with or without food. If a dose of cobimetinib is missed or if vomiting occurs when the dose is taken, resume dosing with the next scheduled dose.

Guidelines for dosage modification and treatment interruption or discontinuation are provided in Section [5.1.3](#).

Any overdose or incorrect administration of cobimetinib should be noted on the Study Drug Administration electronic Case Report Form (eCRF). Adverse events associated with an overdose or incorrect administration of cobimetinib should be recorded on the Adverse Event eCRF (see Section [5.3.5.12](#)).

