Dose reductions of atezolizumab are not permitted. Guidelines for treatment interruption or discontinuation and the management of specific adverse events related to the combination of cobimetinib and atezolizumab are provided in Sections 5.1.3 (see Table 6). Guidelines for treatment interruption or discontinuation and the management of atezolizumab-specific adverse events are provided in Section 5.1.2 and Appendix 8, as well as the Atezolizumab Investigator's Brochure. For anaphylaxis precautions, see Appendix 7.

See the Pharmacy Manual for detailed instructions on drug preparation, storage, and administration.

Any overdose or incorrect administration of atezolizumab should be noted on the atezolizumab administration eCRF. Adverse events associated with an overdose or incorrect administration of atezolizumab should be recorded on the Adverse Event eCRF (see Section 5.3.5.12).

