5.1.3 Management of Patients Who Experience Specific Adverse Events

5.1.3.1 Cobimetinib Dose Modifications

General dose modifications for cobimetinib are provided in [Table 5](#). Dose modifications for specific adverse events are provided in [Table 6](#).

Table 5 Recommended Cobimetinib Dose Modifications

Grade (NCI CTCAE)	Recommended Cobimetinib Dose
Grade 1 or Grade 2 (tolerable)	No dose reduction. Maintain cobimetinib at the same dose of 60 mg QD (3 tablets)
Grade 2 (intolerable) or Grade 3 or 4 (any)	
First appearance	Interrupt treatment until Grade \leq 1, restart treatment at 40 mg QD (2 tablets)
Second appearance	Interrupt treatment until Grade \leq 1, restart treatment at 20 mg QD (1 tablet)
Third appearance	Consider permanent discontinuation.

NCI CTCAE=National Cancer Institute Common Terminology Criteria for Adverse Events;
QD=once daily.

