5.1.3.3 Management of Cobimetinib- and Atezolizumab-Specific Adverse Events

Toxicities associated or possibly associated with cobimetinib plus atezolizumab treatment should be managed according to standard medical practice. See [Appendix 8](#) for management of adverse events related to atezolizumab.

For management of cobimetinib- and atezolizumab-specific toxicities, including IRRs, gastrointestinal toxicity, dermatologic toxicity, hepatotoxicity, pulmonary toxicity, potential eye toxicity, reductions in LVEF from baseline, rhabdomyolysis, elevated CPK, and hemorrhage, see [Table 6](#).

Table 6 Guidelines for Management of Patients Who Experience Specific Adverse Events (Cobimetinib and Atezolizumab)

Event	Action to Be Taken

General guidance for dose modifications and treatment delays and discontinuation
	
 • There will be no dose modifications for atezolizumab. • If atezolizumab is withheld and corticosteroids are initiated for an atezolizumab-related toxicity, corticosteroids must be tapered over ≥ 1 month to ≤ 10 mg/day oral prednisone or equivalent before atezolizumab can be resumed.^{a, b, c} 
The dose of cobimetinib can be reduced by 20 mg (one dose level) up to two times (i.e., from 60 mg to 40 mg and then from 40 mg to 20 mg). If further dose reduction is indicated after two dose reductions, the patient must discontinue cobimetinib but may continue treatment with atezolizumab at the investigator's discretion.
 
 • If atezolizumab is discontinued, treatment with cobimetinib may be continued at the investigator's discretion and after discussion with the Medical Monitor. • If cobimetinib is withheld for > 28 days because of toxicity, the patient should be discontinued from cobimetinib, unless resumption of treatment is approved by the Medical Monitor after discussion with the investigator. • If atezolizumab is withheld for > 105 days because of toxicity, the patient should be discontinued from atezolizumab, unless resumption of treatment is approved by the Medical Monitor after discussion with the investigator.

IRRs, anaphylaxis, and hypersensitivity reaction
	
 • Guidelines for management of IRRs are provided in Appendix 8. • For anaphylaxis precautions, see Appendix 7. • For severe hypersensitivity reactions, permanently discontinue all study treatment.

IRR=infusion-related reaction.

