AST/ALT > $3 \times$ baseline values to < $5 \times$ ULN with total bilirubin < $2 \times$ ULN (Grade 2)	
 • Continue all study treatment. • Monitor LFTs at least weekly. • Consider referral to a hepatologist and liver biopsy. • For suspected immune-related events of > 5 days duration 
 – Consider withholding atezolizumab^a – Consider administering 1–2 mg/kg/day oral prednisone or equivalent followed by ≥ 1 month taper – Restart atezolizumab if event resolves to Grade 1 or better within 105 days.^{b, c} – Permanently discontinue atezolizumab and cobimetinib if event does not resolve to Grade 1 or better within 105 days.^{a, b, c}
AST/ALT > $5 \times$ baseline values to < $10 \times$ ULN with total bilirubin < $2 \times$ ULN (Grade 3)	
 • Continue all study treatment. • Monitor LFTs at least weekly. • Consider referral to a hepatologist and liver biopsy. • For suspected immune-related events: 
 – Withhold atezolizumab – Consider administering 1–2 mg/kg/day oral prednisone or equivalent followed by ≥ 1 month taper – If event does not improve within 48 hours after initiating corticosteroids, consider adding an immunosuppressive agent. If event resolves to Grade 1 or better, taper corticosteroids over ≥ 1 month. – Permanently discontinue atezolizumab and cobimetinib if event does not resolve to Grade 1 or better within 105 days.^{a, b, c}

LFT = liver function test; Q4W = every 4 weeks; ULN = upper limit of normal.

^a Resumption of atezolizumab may be considered in patients who are deriving benefit and have fully recovered from the immune-related event. Patients can be rechallenged with atezolizumab only after approval has been documented by both the investigator (or an appropriate delegate) and the Medical Monitor.

^b If corticosteroids have been initiated, they must be tapered over ≥ 1 month to ≤ 10 mg/day oral prednisone or equivalent before atezolizumab can be resumed.

^c Atezolizumab may be withheld for a period of time beyond 105 days to allow for corticosteroids to be reduced to ≤ 10 mg/day oral prednisone or equivalent. The acceptable length of the extended period of time must be agreed upon by the investigator and the Medical Monitor.

Table 6 Guidelines for Management of Patients Who Experience Specific Adverse Events (Cobimetinib and Atezolizumab) (cont.)

Event	Action to Be take

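### For isolated Grade 3 AST/ALT elevation in Cohorts A and B, Section 5.1.1.1.5 and Table 5 act on cobimetinib while the Table 6 row continues it; the text points to Table 6 but never says it overrides

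*Combined protocol and SAP*

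**What the plan says.** Three places in the combined protocol and SAP bear on cobimetinib when a Cohort A or B patient has a Grade 3 transaminase elevation.

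- **Section 5.1.1.1.5**, in the account of identified cobimetinib risks, ends: "Grade 3 and 4 liver laboratory abnormalities should be managed with dose interruption, reduction, or discontinuation of cobimetinib". It has no cross-reference to Section 5.1.3.3.
- **Table 5 (Section 5.1.3.1)**, the general cobimetinib rule, interrupts the drug for any Grade 3 or 4 event until Grade 1 or better. It restarts at 40 mg after the first occurrence and 20 mg after the second.
- **Table 6 (Section 5.1.3.3)**, in the row it labels Grade 3 (AST/ALT above 5 x baseline to below 10 x ULN, total bilirubin below 2 x ULN), begins "Continue all study treatment" and asks for liver tests at least weekly. The atezolizumab hold, the steroids and the 105-day stop of both drugs all sit under "For suspected immune-related events".

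Several sentences point towards Table 6. Section 4.2.2.1, on cobimetinib dosing, reads "Guidelines for dosage modification and treatment interruption or discontinuation are provided in Section" 5.1.3. Section 4.2.2.2 sends adverse events of the combination to Table 6. Section 5.1.3.1 reads "Dose modifications for specific adverse events are provided in" Table 6. Section 5.1.3.3 lists, among the items managed there, "toxicities, including IRRs, gastrointestinal toxicity, dermatologic toxicity, hepatotoxicity, pulmonary toxicity". Section 5.1 describes the earlier sections differently: "The risks associated with cobimetinib and atezolizumab are detailed in Section 5.1.1 and 5.1.2".

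**The concern.** A site that reads Section 5.1.1.1.5 or Table 5 would hold or reduce cobimetinib. A site that reads the Table 6 row would carry on. Section 5.1.1.2.1 lists severe hepatotoxicity as a potential risk of cobimetinib, and about 60 centers take part (Section 9.4), so contrary dosing instructions invite uneven handling and disagreement over what counts as a deviation.

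There is also a small effect on the safety data. Section 5.3.5.5 makes a laboratory result reportable as an adverse event if it changes study treatment. The same elevation could therefore be recorded at a site that holds the drug and go unrecorded at a site that continues it, unless one of the other reporting criteria is met. Section 6.5 summarizes dose intensity and events leading to interruption, and those summaries would partly reflect which text a site followed.

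**Working it through.** The plan gives no figure to reproduce. The check is a comparison of texts, followed by a rough look at frequency.

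**1. The instructions side by side, for Grade 3 AST/ALT with bilirubin below 2 x ULN**

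| Text | Cobimetinib action |
|---|---|
| Section 5.1.1.1.5, last sentence | interrupt, reduce or discontinue |
| Table 5, general rule | interrupt to Grade 1 or better, restart lower |
| Table 6, Grade 3 row, not suspected immune-related | continue |
| Table 6, Grade 3 row, suspected immune-related | continue; both drugs stopped permanently if not Grade 1 or better within 105 days |

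In the third line, the row offers no cobimetinib action other than continuation. That is where the conflict is cleanest.

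**2. How many rows are affected.** Table 6 has five AST/ALT rows.

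- Grade 1 and Grade 2: outside the last sentence of Section 5.1.1.1.5.
- AST/ALT above 3 x ULN with bilirubin above 2 x ULN: withhold, restart cobimetinib one level lower. Consistent with it.
- AST/ALT above 10 x ULN: permanent stop. Consistent with it.
- Grade 3 with bilirubin below 2 x ULN: contrary to it.

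One row of five conflicts.

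**3. Whether precedence is settled.** Section 5.1.3.1 calls Table 5 general and Table 6 event-specific, so the ordinary reading lets Table 6 displace Table 5. That reading does not dispose of Section 5.1.1.1.5, which is itself specific to liver abnormalities. The hemorrhage and serous retinopathy subsections of Section 5.1.1.1 send the reader to Section 5.1.3.3; the liver subsection gives its own order. Its opening refers to use with vemurafenib, which is not a study drug here, but the instruction is not limited to that setting.

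**4. Frequency.** Section 1.3.5.1.1 lists the Grade 3 or higher events seen in at least 5% of 150 patients in the earlier combination study: fatigue, anemia and diarrhea. An unlisted term therefore occurred in fewer than 0.05 x 150 = 7.5 patients, so at most 7:

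- 7/150 = 4.7% (95% Clopper-Pearson 1.9% to 9.4%).
- Applied to about 102 patients in Cohorts A and B: 102 x 7/150 = 4.8 per term. At the upper confidence limit, 102 x 0.094 = 9.6.

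Among the 22 melanoma patients in that study, one case is 1/22 = 4.5%, which is listed as 5.0%. An unlisted ALT or AST term is thus 0/22 (95% Clopper-Pearson 0 to 15.4%).

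These figures suggest a small number and do not bound it. They are per reported term, and ALT and AST terms may fall in different patients. They count adverse event reports, and the earlier study's rule for reporting laboratory changes is not given. The row is also entered relative to baseline: assuming a baseline of 0.5 x ULN, 5 x baseline is 2.5 x ULN, which lies within the range of the Grade 1 row. In the other direction, reports of Grade 3 or higher would include patients who belong in the two stricter rows.

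**The case against.** The strongest reply is that Table 6 governs by routing. Four sections send cobimetinib dose changes, combination events or hepatotoxicity to Section 5.1.3 or Table 6, and Section 5.1 presents Section 5.1.1 as a description of risks. On that view the last sentence of Section 5.1.1.1.5 merely paraphrases the Table 5 rule. Much of this stands: it would be wrong to infer that the documents are silent on where to look. What they lack is a statement that Table 6 overrides a liver-specific directive elsewhere in the same protocol.

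One could also try to reconcile the texts by continuing at a reduced dose. The row provides no reduction, whereas the bilirubin row states one, and Table 5 would still call for interruption.

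The safety consequence is limited, and this part of the reply stands as well. The row requires liver tests at least weekly. Section 4.4 allows dosing only when laboratory values are acceptable, although it does not define acceptable. Stricter rows cover high bilirubin and AST/ALT above 10 x ULN. Section 5.2.3 requires significant liver toxicity to be reported within 24 hours, and Section 4.5.3 requires treatment to stop for a condition judged to jeopardize safety. No efficacy endpoint is shown to be affected.

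**Conclusion.** The inconsistency is real and narrow: one of five AST/ALT rows, cobimetinib only, Cohorts A and B only. It should be corrected because it concerns a dosing instruction for a drug with a listed liver risk, and correction is cheap. The conclusion takes the protocol's own Grade 3 label on the row at face value.

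Two stronger readings are not supported. A reader might infer that continuing cobimetinib is the mistake and that patients are being exposed unsafely. The documents do not show which instruction was intended, and the routing leans towards continuation. A reader might also take about 5 patients as a ceiling. For the reasons given with the frequency figures, it is not one: the number affected is probably small, but the documents give no firm upper bound for this row.

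**What to change.** The sponsor should confirm which rule is intended and make all three texts agree.

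- **If continuation is intended:** replace the last sentence of Section 5.1.1.1.5 with a reference to Table 6 in Section 5.1.3.3, and state in Section 5.1.3.1 that Table 6 takes precedence over Table 5 where an event has its own row. Changing Section 5.1.1.1.5 alone would leave Table 5 calling for interruption. Alkaline phosphatase has no row in the Table 6 liver section. Treatment-related Grade 3 or 4 elevation would follow the catch-all row at the end of Table 6: withhold all study treatment, resume cobimetinib one level lower if Grade 1 or better within 28 days, otherwise stop it.
- **If interruption is intended:** add to the Table 6 Grade 3 row that cobimetinib is withheld until Grade 1 or better and restarted one dose level lower. Section 5.1.1.1.5 and Table 5 can stay as they are.

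The cost is a few sentences in the next amendment, with no added visits or tests. Section 9.6 applies to either version: IRB/EC approval, and regulatory approval where locally required, before implementation, since neither change is evidently administrative or made to remove an immediate hazard.
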